6.1 STUDY INTERVENTION ADMINISTERED

6.1.1 Investigational medicinal products

Table 3 - Overview of study interventions administered

ARM name	Dupilumab	Placebo
Intervention name	For adults and those adolescents ≥ 60 kg: Dupilumab 300 mg For adolescents ≥ 30 kg and < 60 kg: Dupilumab 200 mg	For adults and those adolescents ≥ 60 kg: Placebo matching dupilumab 300 mg For adolescents ≥ 30 kg and < 60 kg: Placebo matching dupilumab 200 mg
Type	Biological/Vaccine	Other
Dose formulation	
Dupilumab 300 mg: a 150 mg/mL dupilumab solution in a pre-filled syringe to deliver 300 mg in 2 mL.Dupilumab 200 mg: a 175 mg/mL dupilumab solution in a pre-filled syringe to deliver 200 mg in 1.14 mL. 
or
	
Placebo matching dupilumab 300 mg will be supplied as an identical formulation to the active 300 mg formulation without dupilumab, in a pre-filled syringe to deliver placebo in 2 mL. 
or
 
Placebo matching dupilumab 200 mg will be supplied as an identical formulation to the active 200 mg formulation without dupilumab, in a pre-filled syringe to deliver placebo in 1.14 mL.

Unit dose strength(s)	300 mg or 200 mg	0 mg
Dosage level(s)	300 mg every 14 ± 3 days after an initial loading dose of 600 mg or 200 mg every 14 ± 3 days after an initial loading dose of 400 mg	0 mg every 14 ± 3 days after an initial loading dose of 0 mg
Route of administration	Subcutaneous	Subcutaneous
Use	Experimental	Experimental
IMP and NIMP	IMP	IMP

ARM name	Dupilumab	Placebo
Packaging and labeling	Each dose of dupilumab will be supplied as 1 glass pre-filled syringe packed in a participant kit box. Both glass pre-filled syringe and box will be labeled as required per country requirement	Each dose of placebo will be supplied as 1 glass pre-filled syringe packed in a participant kit box. Both glass pre-filled syringe and box will be labeled as required per country requirement

Abbreviations: IMP = investigational medicinal product; NIMP = noninvestigational medicinal product.

The IMP is administered every 14 ± 3 days (q2w) during the 24-week treatment period with the last IMP administration at Week 22.

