8.3.7 Adverse event of special interest

An AESI is an AE (serious or nonserious) of scientific and medical concern specific to the Sponsor's product or program, for which ongoing monitoring and immediate notification by the Investigator to the Sponsor is required. Such events may require further investigation in order to characterize and understand them. Adverse events of special interest may be added, modified, or removed during a study by protocol amendment.

- Anaphylactic reactions
- Systemic hypersensitivity reactions
- Helminthic infections
- Any severe type of conjunctivitis or blepharitis
- Keratitis
- Clinically symptomatic eosinophilia (or eosinophilia associated with clinical symptoms)
- Significant ALT elevation
 - ALT $>5 \times$ the ULN in participants with baseline ALT $\leq 2 \times$ ULN;
or
 - ALT $>8 \times$ ULN if baseline ALT $>2 \times$ ULN.
- Pregnancy of a female participant entered in a study as well as pregnancy occurring in a female partner of a male participant entered in a study with IMP.
 - Pregnancy occurring in a female participant entered in the clinical study or in a female partner of a male participant entered in the clinical study. It will be qualified as an SAE only if it fulfills one of the seriousness criteria (see Appendix 3 [[Section 10.3](#)]).
 - In the event of pregnancy in a female participant, IMP should be discontinued.
 - Follow-up of the pregnancy in a female participant or in a female partner of a male participant is mandatory until the outcome has been determined (See Appendix 4 [[Section 10.4](#)])
- Symptomatic overdose (serious or nonserious) with IMP/Noninvestigational medicinal product (NIMP)

- An overdose (accidental or intentional) with the IMP is an event suspected by the Investigator or spontaneously notified by the participant (not based on systematic pills count) and defined as at least twice the intended dose during an interval of less than 11 days. The circumstances (ie, accidental or intentional) should be clearly specified in the overdose form. An overdose (accidental or intentional) with any NIMP is an event suspected by the Investigator or spontaneously notified by the participant (not based on systematic pills count) and defined as at least twice the maximum prescribed daily dose, within the intended therapeutic interval. The circumstances (ie, accidental or intentional) should be clearly specified in the overdose form.

8.3.7.1 *Anaphylactic reactions*

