4 STATISTICAL ANALYSES

4.1 GENERAL CONSIDERATIONS

This SAP provides a comprehensive and detailed description of strategy and statistical techniques for the summary and analysis of EFC16720.

In general, continuous data will be summarized using the number of observations available, mean, standard deviation (SD), median, minimum, and maximum. Categorical and ordinal data will be summarized using the count and percentage of participants.

The baseline value of efficacy parameters is defined as the last available value up to randomization date and prior to the first dose of study intervention unless otherwise specified. The baseline value of the other parameters is defined as the last available value prior to the first dose of investigational medicinal product (IMP) if the participant is treated, or the last available value up to randomization date if the participant is not exposed to IMP.

Observation period

The observation period will be divided into 4 segments:

- The **pre-treatment period** is defined as the period up to first IMP administration.
- The **treatment-emergent (TE) period** is defined as the period from the first IMP administration to the last IMP administration + 98 days. The treatment-emergent period includes the following 2 periods:
 - The **on-treatment period** is defined as the period from the first IMP administration to the last administration of the IMP + 14 days
 - The **residual treatment period** is defined as the period from the end of the on-treatment period to the end of the treatment-emergent period.
- The **post-treatment period** is defined as the period from the end of the treatment-emergent period.

The on-study period is defined as the time from start of intervention until the end of the study defined as the status date collected on e-CRF page “Completion of End of Study”.

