- Deaths in non-randomized or randomized but not treated participants

Analysis of adverse events of special interest (AESIs) and other AEs of interest

Adverse events of special interest (AESIs) and other AEs of interest will be selected for analyses as indicated in [Table 7](#). Number (%) of participants experiencing at least one event will be provided for each event of interest. Tables will be sorted as indicated in [Table 5](#).

Table 7 - Selections for AESIs and other AEs of interest

AE Grouping	Criteria
AESI	
Anaphylactic reaction	Anaphylactic reaction algorithmic approach (Introductory Guide for Standardised MedDRA Queries (SMQs) Version 18.1): includes anaphylactic reaction narrow SMQ (20000021) terms and programmatic identification of cases based on occurrence of at least two preferred terms meeting the algorithm criteria occurring within 24 hours of each other. The latter cases identified using the algorithm will undergo blinded medical review taking into account the timing of events relative to each other and to IMP administration for final determination of an anaphylactic reaction or not.
Systemic hypersensitivity reactions	SMQ [20000214] hypersensitivity narrow search and [AE corrective treatment/therapy = 'Y' or Action taken with IMP = 'Drug withdrawn' or Action taken with IMP = 'Drug interrupted'] followed by blinded medical review (documented process) for selection of relevant systemic hypersensitivity events
Helminthic infections	CMQ10544 based on HLGT as "Helminthic disorder"
Any severe type of conjunctivitis	CMQ10498 based on PTs (See Section 5.5) ^a and "Severe" ticked in Adverse Events eCRF page
Any severe type of blepharitis	CMQ10497 based on HLGT as "Lid, lash and lacrimal infections, irritations and inflammations" and "Severe" ticked in Adverse Events eCRF page
Keratitis	CMQ10642 based on the following PTs [keratitis, allergic keratitis, ulcerative keratitis, atopic keratoconjunctivitis, herpes ophthalmic, ophthalmic herpes simplex, corneal infection] ^a

AE Grouping	Criteria
Clinically symptomatic eosinophilia (or eosinophilia associated with clinical symptoms) ^b	CMQ10641 based on HLT = Eosinophilic disorders or PT = Eosinophil count increased
Pregnancy of a female patients entered in a study as well as pregnancy occurring in a female partner of a male patient entered in a study with IMP/NIMP	"Pregnancy" or "Partner Pregnancy" checked on the Pregnancy eCRF page as reported by the investigator

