- The exposure adjusted incidence rate by selected SMQ/CMQ and PT showing the number of participants with at least one TEAE per 100 patient-years.

- All TEAEs, by selected SMQ/CMQ including risk differences and hazard ratios with corresponding 95% CIs.
- For each AESI and other selected AE groupings,
 - Number (%) of participants with any specific TEAE
 - Number (%) of participants with any specific serious AE (regardless of treatment emergent status)
 - Number (%) of participants with any specific treatment emergent serious AE
 - Number (%) of participants with any specific AE leading to death
 - Number (%) of participants with any specific TEAE leading to permanent study drug discontinuation
 - Number (%) of participants with any specific TEAE related to IMP reported by investigator
 - Number (%) of participants with any specific TEAE by maximum intensity, corrective treatment, and final outcome
 - Number (%) of participants with any specific TEAE adjusted by the exposure duration
 - Time to onset of first TEAE and cumulative incidence at specified time points (K-M estimates at Week 12 and 24) and K-M plot may be provided to depict the course of onset over time if the number of events is large enough.
 - Number (%) of participants with injection site reactions by the related injection.
 - Number (%) of participants with different number of injection site reactions.
- In addition, AESIs reported by the investigator in eCRF will be summarized separately.

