4.8.2.1 Association of Immunogenicity with Exposure, Safety and Efficacy

The safety and efficacy analysis mentioned below will be conducted using the following categories:

ADA positive participants: Participants with treatment-emergent or treatment-boosted response.

ADA negative participants: Participants with pre-existing immunoreactivity or negative in the ADA assay at all time points.

Impact of ADA on PK profile

Potential associations between ADA variables (e.g., ADA peak titers, neutralizing antibody status, treatment-emergent, persistent, indeterminate and transient response, treatment-boosted) and impact on serum concentration profile of dupilumab may be explored. Plot of serum concentration of functional dupilumab versus visit will be provided by ADA variables for dupilumab group. Individual participant plots of dupilumab concentration according to ADA status will be provided.

Impact of ADA on clinical efficacy endpoints

Associations between the ADA variables (e.g., ADA peak titers, neutralizing antibody status, treatment-emergent, persistent, treatment-boosted) and the primary efficacy endpoint may be explored for the dupilumab dosed group.

Association of ADA with clinical safety endpoints

Association of safety versus ADA status may be analyzed in the ADA population. The safety assessment may focus on the following events:

- Severe injection site reactions last longer than 24 hours or serious injection site reactions
- Hypersensitivity reactions (SMQ (20000214) hypersensitivity narrow search confirmed by medical review)
- Anaphylactic reactions (SMQ (20000021) anaphylactic reaction narrow search)

Associations between ADA variables (e.g., ADA peak titers, neutralizing antibody status, treatment-emergent, persistent and treatment-boosted) and safety may be explored.

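### The systemic hypersensitivity AESI in SAP Table 7 is filtered on treatment or IMP action before blinded review, so the grouped comparison leaves out untreated reactions with no IMP action

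*SAP*

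**What the plan says.** SAP 4.7.2, Table 7, defines the systemic hypersensitivity row as "SMQ [20000214] hypersensitivity narrow search and [AE corrective treatment/therapy = 'Y' or Action taken with IMP = 'Drug withdrawn", with IMP interruption as the third alternative. Blinded medical review follows that selection. Anaphylaxis has its own row, without this condition.

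The Table 7 groupings feed the AESI outputs in the same section, including "All TEAEs, by selected SMQ/CMQ including risk differences and hazard ratios with corresponding 95% CIs" and "Number (%) of participants with any specific TEAE by maximum intensity, corrective treatment, and final outcome". The section also says: "In addition, AESIs reported by the investigator in eCRF will be summarized separately".

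Protocol 8.3.7 is broader. It states that "An AESI is an AE (serious or nonserious) of scientific and medical concern" and lists systemic hypersensitivity reactions with no condition on treatment or IMP action. Protocol 2.3.2 calls systemic hypersensitivity an important identified risk of dupilumab. Protocol 9.4.2, Table 8, leaves the method of identifying AESIs to the SAP.

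For an optional antibody analysis, SAP 4.8.2.1 uses the same search without the filter: "Hypersensitivity reactions (SMQ (20000214) hypersensitivity narrow search confirmed by medical review").

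**The concern.** The condition is joined to the search by *and*, and review comes afterwards. Reviewers therefore never see a narrow-search event that was untreated and led to neither withdrawal nor interruption of IMP, and they cannot restore it. There is no seriousness route either.

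Two outputs are affected. The grouped incidence, with its rate, risk difference and hazard ratio, covers a subset of what the protocol calls the AESI. The corrective-treatment breakdown is conditioned on a variable that also decides entry, so it cannot describe how often reactions needed treatment. At stake is how completely the study report compares the arms on an identified risk. The SAP gives no reason for the filter. The protocol does use a treatment requirement for systemic allergic reactions in its stopping rule (7.1.1) and in its PK/ADA sampling notes (1.3 and 8.5.1.3), which may be its origin.

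**Working it through.** There is no planned figure to reproduce. The check traces an excluded event through the planned outputs and then sizes it.

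**1. The rule.** An event enters review if it is in the narrow search AND (treated OR IMP withdrawn OR IMP interrupted). The excluded set is: narrow search, untreated, not withdrawn, not interrupted.

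**2. Where an excluded event still appears.**

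| Output | Excluded event present? |
|---|---|
| All-TEAE tables and SOC/PT exposure-adjusted rates (SAP 4.7.2) | Yes, no frequency threshold |
| Investigator-reported AESI summary (SAP 4.7.2) | Should be: AESI reporting is mandatory (Protocol 8.3.1), and Protocol 3.1 routes systemic hypersensitivity through AESI/SAE reporting. No blinded review or risk difference is specified for this summary |
| Risk differences and hazard ratios by preferred term (SAP 4.7.2) | Only if the term reaches 5% in an arm |
| Anaphylaxis row (Table 7) | Only if the event qualifies as anaphylaxis |
| Systemic hypersensitivity row and its outputs (Table 7) | No |

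One further route narrows the excluded set. Protocol 7.1.1 requires permanent IMP withdrawal after a systemic hypersensitivity reaction related, or suspected to be related, to the ice cube test, treated or not. Such a reaction during dosing should pass the filter through withdrawal.

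**3. The 5% threshold.** With 39 per arm (SAP section 2, assuming all are dosed as randomized), 1/39 = 2.6% and 2/39 = 5.1%. Two participants in one arm sharing a term get a between-arm estimate. Single participants spread over several terms do not.

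**4. Direction for the treated share.** Let T be confirmed treated reactions, W untreated reactions admitted through IMP action, and U excluded reactions. The reported share is T/(T+W); the share over all confirmed reactions is T/(T+W+U). The reported share is never lower, and it is higher whenever U > 0 and T > 0.

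**5. Size for incidence.** An excluded participant is one whose only confirmed reactions fall in U. Each lowers that arm's incidence by 1/39 = 2.6 points. The risk difference (dupilumab minus placebo) moves by (excluded on placebo − excluded on dupilumab)/39. The documents do not give the number excluded. If it were 0 to 3 per arm (an assumption for illustration only), incidence would fall by 0 to 3/39 = 7.7 points. The risk difference would be unchanged with equal numbers and would move by up to 7.7 points either way if all were in one arm.

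**6. Size for the exposure-adjusted rate.** If all 39 are followed for 252 days (step 7), patient-years are 39 × 252/365.25 = 26.9, and one participant is 1/26.9 = 3.7 per 100 patient-years. If follow-up stopped at Week 24 for everyone (168 days), patient-years are 39 × 168/365.25 = 17.9, and one participant is 5.6. Both ignore drop-out and the cut in patient-years at a first event.

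**7. After the last dose.** The treatment-emergent period "is defined as the period from the first IMP administration to the last IMP administration + 98 days", and dosing is planned "with the last IMP administration at Week 22".

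- Last dose: Day 1 + 154 = Day 155.
- End of period: Day 155 + 98 = Day 253, so the period is 252 days and the window after the last dose is 98/252 = 38.9%.
- SAP 4.9 locks the database for the study report when all participants have completed the 24-week treatment phase. A completer who reaches Week 24 (Day 169) at that lock has 169 − 155 = 14 days after the last dose, out of 168 (8.3%).

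If action taken is coded not applicable once no dose remains, only treated events can enter in this window. The documents do not state that coding.

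**The case against.** The strongest case for the plan is that this is a permitted choice with little consequence. The protocol delegates the method, safety analysis is descriptive with no testing (SAP 4.7), and the excluded reactions are the mildest group: not anaphylaxis, not treated, no IMP action. They remain in other tables. A wider row also has its own hazard. Protocol 8.3.6 has unexpectedly worsened cold urticaria and new or worsened angioedema reported as AEs. If dupilumab works, placebo may have more of these, and a wider row could mix an efficacy difference into the hypersensitivity comparison. All of this stands. It lowers the weight of the point and shapes the fix, but it does not supply the missing grouped comparison.

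A reader might infer more than the documents support:

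- *The SAP breaches the protocol.* It does not, because Protocol 9.4.2 leaves identification to the SAP.
- *Untreated reactions vanish from the report.* They do not; see the table under the working.
- *About 39% of events are lost.* That figure is a share of calendar time for a fully followed completer. It is neither a share of events nor a bias, and it rests on an unstated coding convention.
- *SAP 4.8.2.1 contradicts Table 7.* That analysis is optional and concerns hypersensitivity reactions in general, not systemic ones. It shows only that review without the filter is workable.
- *The filter favours dupilumab.* Nothing in the documents says in which arm excluded events would fall.

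**Conclusion.** The point holds in a limited form. Table 7 adds an entry condition that the protocol's AESI list does not carry, and it applies before blinded review. The Table 7 incidence of systemic hypersensitivity can therefore be too low, and its treated share too high, to the extent that confirmed untreated reactions with no IMP action occur. Whether any occur, how many, and in which arm is unknown. Each affected participant is 2.6 points of one arm's incidence, assuming 39 dosed per arm. What the report would lack is one grouped, blinded-reviewed comparison covering reactions scattered over several preferred terms. This is an improvement to a descriptive summary and not the correction of an error; no test, power or alpha is affected.

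**What to change.** Keep the filtered row as defined and add a second row beside it. Send all treatment-emergent events from the narrow search 20000214, and all investigator-reported systemic hypersensitivity AESIs, to the same blinded review regardless of treatment or IMP action. Have the reviewers classify cold-triggered or disease-related events separately, so that an efficacy difference does not enter the drug-hypersensitivity comparison. Report the confirmed set with the same count, exposure-adjusted rate, risk difference, hazard ratio and corrective-treatment breakdown. State the reason for the filter, and footnote which row feeds the overview line for any treatment-emergent AESI.

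Table 7 already pairs restricted and unrestricted groupings in this way: severe conjunctivitis beside conjunctivitis groupings with no severity condition, and serious or severe injection site reactions beside all injection site reactions.

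The cost is a few SAP sentences, one table row and somewhat more blinded review in a 78-participant study, with no new data. The new row leans more on reviewer judgement, which is why it should sit beside the filtered row and not replace it. If nothing was excluded and no event is classified as disease-related, the two rows will agree.
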